Phase Three: Following recruitment, a research associate not otherwise involved in the study will screen participants prior to enrollment. Veterans will be randomized in a 1:1 ratio, with a research staff member utilizing and keeping the schedule. Veterans randomized to VACT-CP (and online website that includes 7 online-module based weekly sessions of treatment) via personal computer or provided laptop at the Bedford VAMC. Veterans in the waitlist control will be provided with a list of common pain resources at the Bedford VAMC. The VACT-CP program will be housed on a secure web server through Northeastern University, with no Veteran private health information collected by the system. Veterans in both conditions will complete the assessment battery (see Table 2 for specific schedule) at baseline, either in-person or remotely (via a phone call or online using the VA-approved Qualtrics survey platform) depending on the participant’s preference. In addition, the full battery of primary outcomes and process measures will be taken at mid-point of the intervention phase (3 weeks) and at the end, immediately following the treatment (7 weeks). Veterans will be tracked in terms of their post-referral treatment engagement (e.g., enrolling in any of the pain-resource options on the handout). In addition, a research associate will call the Veteran at weeks 3 and 6 and conduct a brief safety assessment with Veterans assess for potential suicidality, usability issues, and participant health and well-being.

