During each wave of testing, Veterans will interact with the VACT-CP online treatment to: 1) gather feedback regarding acceptability and usefulness of the treatment, 2) gather and analyze complementary data from SUS-8, 3) address any technological issues as they arise, and 4) examine preliminary data from this phase of the study. Modifications to the website will be based upon: 1) acceptability and feasibility of the online treatment, and 2) qualitative feedback obtained from patients, therapist, and mentors. Individual feedback sessions at the end of Phase 2 will be held to gather information for refining the treatment intervention and make it acceptable to patients.

We anticipate that our Veteran intervention reviewers might miss bugs or other user interface problems and anticipate that some revisions to the online system and program may need to be made. For instance, one potential issue that may arise might be an inability for the Veteran to read the text on the screen. After receiving this information during an initial feedback round, the researchers will amend the program with a potential solution, i.e., text size or text color being altered, with the revised version then being piloted in the next round of Veteran user testing. Some usability challenges will be addressed with introductory handouts/tutorial materials/orientation to the program at the beginning of the intervention session. In addition, large organizational issues will be discussed before moving on to platform refinement.

Phase 3: Data Collection

Callers will be initially screened by phone. Eligible participants will be scheduled for an in-person assessment or phone-conference with research staff. At this assessment, research staff will confirm study eligibility and obtain informed consent and administer the Structured Clinical Interview for DSM-5

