Phase Three: We will aim to recruit up to 60 participants over fifteen months total to allow for the desired final 40 participants screened as eligible and randomized into the pilot RCT study, specifically aiming for recruiting 3-4 participants per month. Subjects for the proposed study will be recruited over the course of approximately 15 months and be screened according to their presence of chronic pain and other inclusion/exclusion criteria. First, potential participants will be pre-screened by phone to determine whether basic study eligibility criteria are met. Individuals who remain eligible after the phone pre-screen will be randomized in a 1:1 ratio. Veterans randomized to VACT-CP will receive 7 online-module based weekly sessions of treatment via personal computer or provided laptop with wireless accessibility at the Bedford VAMC. Veterans in the waitlist control will be provided with a list of common pain resources at the Bedford VAMC. Subjects will be paid \$60 for the baseline assessment, \$40 at the midpoint testing visit/week 3 for waitlist control, and, \$60 for the end of treatment (Session 7)/end of week 7 for control group participants and \$40 for a one-month follow-up (total; \$200 total).

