before any information is collected, or any questionnaires answered, a study staff member will speak with the Veteran by phone or using HIPAA-compliant Skype/Cisco and will review the informed consent with them. We will go over all the elements of informed consent and make sure they are aware of each component. We will then verbally consent Veterans who will then be randomized 1:1 via a previously created randomization schedule to VACT-CP or into Wait-list control.

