It will be the responsibility of the PI to assure that informed consent is obtained from each participant prior to the performance of any protocol procedures, and in accordance with current state and federal regulations. A waiver of documentation of informed consent will be requested as individuals will be consented verbally. The informed consent process will be completed prior to the initiation of any study procedures. When obtaining consent, we will communicate basic facts about the study, such as the expected duration (30 minutes for baseline assessments and 1 hours to test the VACT-CP program and interview, and 25 minutes for post-usability testing surveys), the intended use of the data, and who is funding the study. We will review the information sheet and ask if they have any questions. We will assure the privacy of participants by asking them to use a private space, rather than a shared office or common area, to speak with us.

Phase Three: Verbal informed consent will be obtained from each participant prior to entering the study. The information sheet provided to Veterans will explain in simple terms, before the patient is entered into the study, the risks and benefits to the patient. Verbal consent will be obtained after a thorough explanation of the study by the PI or other study personnel (e.g., research assistant,

postdoctoral fellow, PI), and an opportunity for the participant to ask questions about the study. This discussion will take place under conditions in which the participant has adequate time to consider the benefits and risks associated with his/her participation in the study.

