4.6.2.1 Data Security

How/where informed consent documents and study data will be stored:

All data collected for recruitment and for screening purposes will be filed separately from any potential identifying information for each subject. All data will be filed securely under lock and key in file cabinets at the Bedford VA Hospital (Building 5, Room 135b). Data files related to study participation, including participant data and informed consent documents, will be stored directly on a VA-secure server designated for this study only by anonymous subject study number, will be securely maintained, and will be assessable only to research staff directly involved in this project. Upon completion of the study and data entry and analysis, all data and files will be stored and archived indefinitely under lock and key, or on the designated secure server. All hard-copies of non-sensitive study documents will be secured in locked file cabinets within locked SoCRR (Social & Community Reintegration Research) offices in Building 5 (Room 135b) at the Bedford VAMC.

Electronic files and data will be de-identified and labeled with the study ID number, and then stored in a password-protected file on a VA server folder (<\\R04BEDNAS21.v01.med.va.gov>) (specific to this study). Storage will be in accordance with VA Research Data Security and Privacy requirements. De-identified data will be labelled only with a non-identifying study subject number. Data files will be securely maintained, and will be accessible only to research staff directly involved in this project. All video recordings will be stored on the server and accessible only to study personnel for fidelity monitoring purposes.

De-identified questionnaire data for this study (if not collected by Qualtrics) will be stored in a database called REDCap (Research Electronic Data Capture), which is housed on a VA-secured, VA Informatics and Computing Infrastructure (VINCI) server at the Austin Information Technology Center (AITC). To ensure the protection of Veteran data, VINCI maintains compliance with the guidelines set forth by Veterans Health Administration (VHA) Handbook 1200.12, Use of Data and Data Repositories in VHA Research, and all other applicable VA and VHA policies and regulations. In addition, VINCI has undergone all security certification activities in support of obtaining an Authorization to Operate (ATO). Access to VINCI resources are approved in accordance with the requirements of National Data

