4.6.2.2 Data Safety Monitoring

A DSMB is not required because multiple clinical sites will not be used, the study is not blinded, and interventions are not particularly high risk or vulnerable populations are not included.

Data and safety monitoring plan:

[name] will be monitoring adverse events involving data loss and adverse events related to the study. Adverse events will be monitored in the following ways:

- 1) Many elements of the research plan are intended to minimize the risks of study participation. Co-investigators will be available to subjects in the event of an emergency. In the event that serious medical or mental health complications should occur, consultation from emergency clinical services is immediately available at the Bedford VA Hospital.
- 2) Weekly meetings will be held between Drs. [name] and [name]. We will discuss and resolve any safety issues more frequently if necessary, as such issues arise, possible participant withdrawal from the study, or any safety concern.
- 3) Drs. [name] and [name] will observe and ensure that data are locked in designated file cabinets and data stored electronically are password-protected and not moved outside the VA. Data integrity and confidentiality will be safeguarded as discussed in the Data Management section of the application and under Protection Against Risks above.
- 4) Data integrity and confidentiality will be safeguarded as discussed in the Data Management section of the application and under Protection Against Risks above. We will report data security incidents to the IRB, privacy, and information security (e.g., theft or loss of data or storage media, unauthorized access of sensitive data or storage devices or non-compliance with security controls) as soon as we learn of these incidents.

Reporting Adverse Events: Reporting of adverse events will occur as follows:

Local Research Deaths. The IRB will be notified immediately upon becoming aware of any local research death that is both unanticipated and related to the research. A written notification to the IRB will be submitted within

5 business days of becoming aware of the death. If the death does not appear to be both unanticipated and related to the research, it will be recorded and reported at continuing review.

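### No allocation concealment is described for Phase 3, and the keeper of the pre-made schedule is not separated from the unblinded staff who confirm eligibility and take consent

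*Combined protocol and SAP*

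**What the plan says.** On handling the list, section 3.3 (Phase Three) states: "Veterans will be randomized in a 1:1 ratio, with a research staff member utilizing and keeping the schedule". Section 4.5.1b, on Veterans consented remotely, states: "We will then verbally consent Veterans who will then be randomized 1:1 via a previously created randomization schedule to VACT-CP or into Wait-list control". Section 4.6.2.2 gives as one reason for having no DSMB that "the study is not blinded".

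On who decides whether a Veteran enters, there are three statements:

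- Section 3.3: "a research associate not otherwise involved in the study will screen participants prior to enrollment".
- Section 3.4 (Phase 3), on the assessment that follows the phone screen: "research staff will confirm study eligibility and obtain informed consent and administer the Structured Clinical Interview for DSM-5".
- Section 4.5.2b (Phase Three): "Verbal consent will be obtained after a thorough explanation of the study by the PI or other study personnel". The same section has the staff member judge whether the Veteran is competent to consent.

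On timing, section 4.1 (Phase Three) gives a different order from section 4.5.1b: "Individuals who remain eligible after the phone pre-screen will be randomized in a 1:1 ratio".

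The protocol mentions no sealed envelopes, no central or electronic release of allocations, no method of generating the sequence and no block size. It does not say who creates the list.

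**The concern.** Concealment keeps the next assignment unknown until a participant is irrevocably in the trial. It matters most in an open study, where it is the main protection against selective entry. Here one person both holds and operates a complete list, and the text puts no barrier between that person and the staff who decide on entry.

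Those decisions leave room for judgement. Section 4.4 excludes Veterans for cognitive impairment, for clinical features needing a higher level of care, and for impairment that would hinder using a computer. Section 4.5.2 expects a third of those consented to prove ineligible. Someone who knew that the next slot was VACT-CP could, without intending it, pass a motivated and technically comfortable Veteran or defer a doubtful one.

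Such steering would affect what Phase 3 reports under section 3.5: the proportion completing at least 5 modules, retention in each condition, the check that the groups are equivalent, and the pre/post descriptions by arm. That section also uses the results to plan the efficacy trial. With 40 participants, analysis could not reliably repair the damage.

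**Working it through.** The plan gives no figure on concealment to reproduce. Its one power figure (n=125 for a medium effect, section 3.5) is met closely by 63 per arm, 126 in total, if medium is taken as d = 0.5. This point does not depend on it.

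**Step 1: who acts at each stage.**

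| Stage | Section | Person named |
|---|---|---|
| Screening before enrolment | 3.3 | A research associate outside the study |
| Eligibility confirmed, SCID-5 | 3.4 | Research staff |
| Consent, judgement of competence | 4.5.2b | PI or other study personnel |
| Keeping and using the list | 3.3 | A research staff member, not further identified |

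The second and fourth rows use the same general description. Nothing says that they are different people, and nothing says that they are the same.

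**Step 2: how many are turned away after consent.** Section 4.5.2 gives a maximum of 60 consented, of whom 2 in 3 prove eligible: 60 × 2/3 = 40 enrolled and 60 − 40 = 20 not. Up to 20 exclusions therefore fall after consent, where the independent screener is not described as acting.

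**Step 3: the order of events.** Section 4.5.1b puts consent before randomisation. Section 4.1 puts randomisation directly after the phone pre-screen. Taken literally, section 4.1 makes the independent screener the last gate, but then consent and the SCID-5 exclusions would come after the allocation is known. Neither order, as written, hides the allocation until eligibility is settled. The section 4.5.1b sentence covers remote consent only; there is no matching sentence for Veterans consented in person.

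**Step 4: sensitivity (illustration, not an estimate).** Inputs: 20 per arm (section 3.5); k pairs exchanged between arms; an assumed gap of D SD in prognosis within each pair. The documents supply neither k nor D.

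- Each exchange moves each arm mean by D/20 in opposite directions, so the shift in the difference is 2kD/20.
- k = 0: shift 0.
- k = 1, D = 1: 2 × 1/20 = 0.10 SD. With D = 0.5: 0.05 SD.
- k = 2, D = 1: 0.20 SD.
- For a proportion, exchanging one Veteran who would be retained for one who would not moves each arm by 1/20 = 5 percentage points, and so the difference in retention by 10 points. Module completion in the VACT-CP arm would move by 5 points per such exchange.

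**Step 5: why hiding the list is not enough with fixed blocks.** In an open study, past allocations are known. With fixed blocks of known size b, guessing the arm that is behind is right with expected frequency 0.5 + (2^b / C(b, b/2) − 1)/(2b). This gives 75% for b = 2, 71% for 4, 68% for 6, 67% for 8 and 59% for a single block of 40. Simple randomisation gives 50%. The block sizes are assumptions. Randomly varied, undisclosed sizes withhold the block boundary on which these rates depend.

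**The case against.** The strongest reply is that the protocol nowhere says the list keeper consents or enrols anyone. Section 4.5.1b is in the passive and does not name the randomiser, so a single designated keeper who stands apart from enrolment fits the text equally well. This stands. A reader might infer that enrolling staff can see the next allocation, or that the plan sets out the opposite of concealment. The documents do not support either reading: they are silent on both.

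Second, the screener is independent, and because section 4.5.2 treats a Veteran as enrolled only after consent and eligibility, screening before enrolment might extend beyond the phone call. This stands only in part. Section 3.4 assigns confirmation of eligibility and the SCID-5 to research staff, and the safeguard is stated for screening alone. It is fair to add that the SCID-5 is a structured interview, so not every exclusion is loose discretion.

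Third, this is a 40-person pilot. Section 3.5 limits outcomes to means and standard deviations, and the Aim 3a analyses are correlations of usability with use, not arm contrasts. This limits the consequence, and the shifts above should not be set against the medium effect in the power paragraph, which the plan says is beyond this study. Retention by condition, module completion and the arm descriptions remain exposed.

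Finally, chance imbalance under simple randomisation is a separate matter. It is not failed concealment and forms no part of this point.

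**Conclusion.** The point holds as a gap in the stated procedure, not as demonstrated bias. A research staff member keeps and uses a pre-made list in an open study, no concealed release is described, the keeper is not separated from those who confirm eligibility and take consent, and two sections disagree on when randomisation happens. Selective entry therefore cannot be ruled out.

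Its size is unknown and may be zero. The 0.10 SD per exchanged pair rests on an assumed 1 SD gap and arms of 20, and the 10-point retention shift on one exchange of a retained for a non-retained Veteran. Neither says how often steering would occur. If separation already exists in practice, the change only documents it. It is worth making because it is cheap and protects the feasibility figures that will shape the next trial.

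**What to change.** Replace the randomisation sentence in section 3.3 with wording to this effect:

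- The 1:1 schedule, in randomly varied blocks, is generated and held by an existing team or programme member with no role in Phase 3 recruitment, eligibility confirmation, consent or assessment. Block sizes are not disclosed to enrolling staff.
- Allocations are released one at a time, and only after consent, confirmed eligibility and baseline assessment have been recorded for that Veteran.
- Release is through the REDCap randomisation function if available, or otherwise by sequentially numbered, opaque, sealed envelopes. Section 4.6.2.1 describes REDCap only as a data store, so availability must be checked.

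Amend sections 4.1 and 4.5.1b to state the same order, for both remote and in-person consent. The cost is minor set-up work and a protocol wording amendment.

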3.4 Data Collection

Phase 1 Data Collection: Data collection after enrollment and during the demo session will consist of 1) a short survey which will not be audio-recorded and 2) a qualitative interview, which will be audio recorded. Confidential and private spaces at the VA Bedford Healthcare System will be used for the assessments. The questionnaire and qualitative interview will take approximately 1 - 1.5 hours total. Demographic questions will be asked regarding age, ethnicity, race, gender identity, and education, as there is research suggesting that personal comfort with technology relates to individual’s interest in referring other to specific technologies (Hilty et al., 2006), and that comfort with technology can be impacted by demographic factors (Czaja et al., 2006; Jackson et al., 2008). The purpose of these questions is to gather information from valuable stakeholders and potential referral-providers on VACT-

CP system to address refinement of the program, possible benefits, barriers, referral concerns, and overall thoughts on the VACT-CP system (see Qualitative Interview Protocol for specifics).

Quantitative Measures

1. **Demographics questionnaire:** will gather basic, non-identifying information including participant age, ethnicity, race, and education (2 minutes).
2. **Work-history survey:** using questions created specifically for this study, we will gather basic information related to working with patients who have chronic pain, including provider's current position, past experiences as a health or mental-health provider specific to working with chronic pain, length of time in current position, past specialized training on treating chronic pain, and information related to making referrals to online or tech-mediated health interventions or resources (4 minutes)

Qualitative Data Gathering

This interview will include open-ended questions related to palatability of the intervention, feasibility of engagement with Veterans with chronic pain, interest or potential concerns with referring Veterans to such a program, and reactions to a short walk-through of the intervention. Questions for palatability (Table 1) are based on the “organizational perspective” components of the Practical, Robust Implementation and Sustainability Model (PRISM: Feldstein & Glasgow, 2008). Interviews will be audio recorded and transcribed.

Table 1. Provider Assessment Interview Structure.

GENERAL INTERVIEW GOALS	
Part 1. Descriptive questions: demographics, history of clinical work with Veterans, past experience with Veteran referrals for chronic pain and inclusion of technology (i.e., mobile apps.) in treatment.	
Part 2. Present the participant with a walk-through of the VACT-CP website prototype and user interface. Using a “think aloud” strategy, ask them to give their immediate thoughts out loud as they interact with the system. Ask clarifying questions as appropriate.	
Part 3. Open-ended questions related to palatability from a current provider or as a potential referral source perspective will be asked.	
PROVIDER ELEMENT	OPEN-ENDED QUESTIONS FOR PROVIDERS
General	What do you think about online programming for Veteran support for chronic pain in general? What are your overall thoughts on VACT-CP?
Patient centeredness	How do you think Veterans could benefit from the program online?
Provides patient choices	For what reasons might you refer Veterans to this program as an option for CP treatment? Are there any Veterans that you would not refer to this type of program because you don't think they would engage or benefit?
Addresses patient barriers	In what ways might you feel comfortable referring a Veteran to this program? What might be some barriers to referring a Veteran to this online program?
Additional program elements	Do you think the provided handout on this intervention would give you enough information to refer Veterans to this intervention? What would you change

	about these materials?
Burden/Barriers	What do you see as potential barriers to referral, or for Veterans to sign up for this online treatment?
Feedback of results	Would you be interested in hearing about VACT-CP results after the study ends?

VACT-CP Revision: Following data collection, we will: 1) gather feedback regarding acceptability and potential usability of the platform in other settings (e.g. at the Veteran's home), 2) gather and analyze provider feedback on the VACT-CP system, 3) address any technological or system-specific concerns as, and 4) use this data to modify potential plans for a future VACT-CP usability pilot. Modifications to the interface and protocol will be based upon: 1) acceptability and feasibility of the VACT-CP platform and potential treatment components, and 2) qualitative feedback obtained from providers. We will not be gathering information on the usefulness of treatment as part of this study.

Individual feedback sessions at the end of the full study will be analyzed together to gather information for refining the treatment to make it acceptable to patients. After receiving the totality of information from 10-12, the researchers will amend the program with a potential solutions i.e, adding VA-specific pain information, text size or text color being altered. Some platform usability and intervention-specific challenges will be addressed with introductory handouts/tutorial materials/orientation to the program at the beginning of the intervention session.

Phase 2: Data Collection:

Qualitative Combined Usability and Contextual Interview. We will focus on usability and feasibility for Phase 2. During the 2 hour at-home usability sessions, participants will assess the usability of the VACT-CP intervention using a “think-aloud protocol”, verbalizing their thoughts as they navigate the website and Coach Anne. After a period of exploration with the site, the research staff will use a pre-created protocol to ask Veterans to interact with Coach Anne through one of the VACT-CP modules (i.e., responding to her queries, entering therapy goals, completing in-session assessments, interacting with the virtual therapist generally). As the participant navigates the intervention website on their computer, their actions will be recorded through a screen-share recording electronically, and the Veterans comments will be recorded via the audio. [name] will observe the actions in real-time during the session via the same technology platform.

Usability Assessment Procedures

Eligible Veterans will first complete baseline demographic and health measures provided over the phone (approximately 30 mins). Following the baseline assessment, Veterans will be provided with a quick overview of the site and interaction system to help Veterans access and understand different portions of the user interface and treatment set-up, during which time they will be asked questions and recorded as a usability interview. Next, Veterans will be provided with verbal instructions for use, and begin their walk- through of a portion of the treatment (approximately 10 mins). During this time, the Veterans will take part in a contextual interview wherein Veterans move through the system unguided and are observed and asked questions about their experience (approximately 30 minutes). After this, additional, usability items (25 mins) and open-ended questions will be asked regarding Veteran preferences (approximately 20 minutes).

For purposes of feedback and iterative program development, the Veteran will only be provided a portion of the VACT-CP program during this time, during which time their use of the system will be recorded. Approximately 4-5 Veterans will be recruited and participate in this usability testing at a time, with 3 different usability testing arms, in order to allow for time to iteratively address any functionality issues or concerns with the user interface. Following this walkthrough, participants will be provided with measures of demographics, usability and health information technology use, including a retrospectively worded version of the Usability Survey items (e.g., I enjoyed using the VACT-CP program) and a semi-structured qualitative exit interview. Participants will receive a \$40 gift card for their virtual research session, which should take approximately 2 hours.

Assessment Measures At Beginning of Session

A broad range of reliable and valid measures will be used to provide an assessment of chronic pain difficulties, demographic information, and technology use, technology interest, and comfort.

Demographics, functional health, and pain measures. Demographic measures will include pain-related information regarding type and duration, age, gender, race and ethnicity, and education. Well-being measures will include psychological depression, Patient Health Questionnaire-9 (PHQ-9), and PTSD Check List (PCL-5), as well as pain interference (Brief Pain Inventory), and the Veteran's RAND 36 Item Health Survey (VR-36). These measures will be used to describe the sample and will take approximately 30 minutes).

Media and Technology Usage and Attitudes Scale (Rosen et al., 2013): A 16-item measure of different attitudes toward technology using a 10-point frequency scale from Never (0) to All the Time (10) that assess comfort level, attitudes towards new technology, and usage patterns for mobile technology. Completed before usability/platform interaction session.

Post-Website Usability Interaction Measures

Intrinsic Motivation and Perceived Usefulness Scale (ITAM; Venkatesh, 2000): The usability survey items were adapted from an existing set of usability questions to make the questions specific to the VACT-CP online treatment. The items form 2-4 item subscales that will be used to address relationships between elements of our modified Integrated Technology Acceptance Model. We will assess antecedent conditions that are proposed to influence health-technology acceptance and use, including satisfaction with medical care, preferences for seeking information, health care needs, internet dependence, and health care knowledge. In addition, we will assess intrinsic motivation, perceived ease of use, and perceived usefulness of each health-technology. Prior versions of the subscales have shown good internal consistency reliability for each subscale (Cronbach's alphas > 0.7 for all but information seeking preference which was 0.60).

System Usability Scale (SUS; Brooke, 1996): a 10-item measure, scored on a 5-point Likert scale, that assesses human-computer interaction. A SUS score above 58 is regarded as above average, and a SUS score above 80 is regarded as high and a score above which participants are likely to recommend the product to friends. The SUS generates a subjective evaluation score using a globally accepted scale and to understand if the system in its current form is sufficiently usable.

Qualitative Combined Usability and Contextual Interview: Veterans will be observed while interfacing with the VACT-CP system, recorded, and asked questions by the interviewer. This will consist of specific questions related to the different parts of the system the veteran interacts with (e.g., the virtual coach design, structure of the modules, feedback system) as well as more open-ended questions when not provided with specific cues (e.g., what are you trying to get to from this page, what could be better about how this is set-up, etc.). Questions will be open-ended in nature, and address the extent of any problems with accessing and using the VACT-CP treatment online, how they might perceive the usefulness or importance of VACT-CP focal areas of treatment, whether they would recommend this treatment to a fellow Veteran, and any problems or concerns they may have with using the VACT-CP program.

Using this additional, open-ended interview protocol, we will also inquire as to whether they would be interested in using the VACT-CP treatment at home beyond this session, and the role of their virtual coach in the patient's interest in the treatment, and about past strategies or tools the patient used to address their chronic pain or tools the patient used to address their chronic pain issues and whether the VACT-CP treatment might seem more useful than prior options or strategies. Finally, participants will be asked to indicate what, if any, changes they would make to the treatment to assist in self-management of their chronic pain. This will also include assessing their interests in complementary and alternative methods of pain management (stretching, yoga, progressive muscle relaxation, etc.) to assess if it would be useful and feasible to add these options to the platform later if desired. The interview will be video-recorded and coded to look for similar themes, difficulties, revisions, and strengths of the system.

Intervention Revision

During each wave of testing, Veterans will interact with the VACT-CP online treatment to: 1) gather feedback regarding acceptability and usefulness of the treatment, 2) gather and analyze complementary data from SUS-8, 3) address any technological issues as they arise, and 4) examine preliminary data from this phase of the study. Modifications to the website will be based upon: 1) acceptability and feasibility of the online treatment, and 2) qualitative feedback obtained from patients, therapist, and mentors. Individual feedback sessions at the end of Phase 2 will be held to gather information for refining the treatment intervention and make it acceptable to patients.

We anticipate that our Veteran intervention reviewers might miss bugs or other user interface problems and anticipate that some revisions to the online system and program may need to be made. For instance, one potential issue that may arise might be an inability for the Veteran to read the text on the screen. After receiving this information during an initial feedback round, the researchers will amend the program with a potential solution, i.e., text size or text color being altered, with the revised version then being piloted in the next round of Veteran user testing. Some usability challenges will be addressed with introductory handouts/tutorial materials/orientation to the program at the beginning of the intervention session. In addition, large organizational issues will be discussed before moving on to platform refinement.

Phase 3: Data Collection

Callers will be initially screened by phone. Eligible participants will be scheduled for an in-person assessment or phone-conference with research staff. At this assessment, research staff will confirm study eligibility and obtain informed consent and administer the Structured Clinical Interview for DSM-5

(SCID-5) to assess for potential psychosis, substance use disorders, or clinically-significant suicidality. Eligible subjects will then complete self-report measures. Participants with additional, co-morbid pain diagnoses will not be excluded. Data will be collected at baseline, the study midpoint (approximately 3 weeks), end of treatment/7 weeks, and at the one-month follow-up period. Self-report baseline and post-baseline assessments will be administered either in-person or online by Qualtrics, a VA-approved platform and vendor. Length of time for assessments will take approximately 2 hours for baseline assessments, 1.5 hours for the mid-point survey, approximately 2 hours for the 7 week/post-intervention surveys, as well as approximately 1 hour for the 1 month follow-up surveys. See Table 2 for the measurement schedule:

Table 2: Measurement Schedule for Phase 3

MEASURE	BASELINE	MIDPOINT	INTERVENTION END /7 WEEKS	1-MONTH FOLLOW- UP
Demographics	X			
MEAQ	x		x	x
CPVI	x	x	x	x
PHQ-9	x	x	x	x
VR-36	x	x	x	x
POQ-SF	x	x	x	x
SCID-5	x			
BPI	x			
CPAQ	x	x	x	x
Usability survey*			x	
SUS*			x	
WAIS-S*			x	
CSQ-8*			x	
Qualitative Interview			x	

*will only be assessed in invention group

Demographics, functional health, and pain measures.

Demographic measures will include age, gender, race and ethnicity, and education. We will also include questions related to medications currently being used for the management of physical or psychological conditions, self-reported using a single-item listing diagnoses, and at baseline and 7 weeks conduct a CPRS record review for such information. These measures will take approximately 10 minutes.

Feasibility and

Acceptability Measures: Feasibility outcomes will include recorded information on recruitment rates, retention rates within each condition, measure completion rates, how often Veterans access the website, and any reported problems with the website. This information will be collected by the research team.

Quality of Life. *The Veteran's RAND 36 Item Health Survey (VR-36)*⁴³ is 36-item measure of health including physical functioning, role limitations due to physical problems, bodily pain, general health perceptions, vitality, social functioning, role limitations due to emotional problems, and mental health. It is often summarized into (physical functioning components and mental functioning components, and is one of the most widely utilized and valid measures of physical and psychological well-being. This survey will take approximately 15 minutes.

Usability Survey. The usability survey items were adapted from an existing set of usability questions to make the questions specific to the VACT-CP online treatment. The items form 2-4 item subscales that will be used to address relationships between elements of our modified Integrated Technology Acceptance Model.³⁵ We will assess antecedent conditions that are proposed to influence HIT

acceptance and use, including satisfaction with medical care, preferences for seeking information, health care needs, internet dependence, and health care knowledge. In addition, we will assess intrinsic motivation, perceived ease of use, and perceived usefulness of each HIT. Prior versions of the subscales have shown good internal consistency reliability for each subscale (Cronbach's alphas > 0.7 for all but information seeking preference which was 0.60). The usability survey should take the average user about 5-7 minutes.

System Usability Scale (SUS; Brooke, 1996) a 10-item measure, scored on a 5-point Likert scale, that assesses human-computer interaction. A SUS score above 58 is regarded as above average, and a SUS score above 80 is regarded as high and a score above which participants are likely to recommend the product to friends. The SUS generates a subjective evaluation score using a globally accepted scale and to understand if the system in its current form is sufficiently usable.⁴⁴ This survey will take approximately 3 minutes.

